## Procedures

All participants in both groups will make a total of 3 visits over a 16-week period. The 2nd visit is at week 4 and 3rd visit at week 16 after initial visit. At each visit, all patients will have a blood test for A1c, CMP, CBC, fasting lipid and measurements of body weight, height, blood pressure, and heart rate, answered adverse reaction questions and completed the Diabetes Medications Satisfaction (DM-SAT) Questionnaire form.

At first visit, the following changes will be made in intervention group:

- (1) All prandial insulin injections (Humalog, Novolog, Apidra, Novolin R or Humulin R) will be discontinued.
- (2) Basal insulin (NPH, Lantus, Levemir, Toujeo or Tresiba) will be continued at 80 % of the home dose. The dose will be gradually increased until the patient is back on the home dose (the dose that the patient has been taking at home prior to the enrollment) or fasting BG of 80-130mg/dl was achieved by using the self-titration regimen. (Attachement#1)
- (3) If the patient is on pre-mixed insulin 2-3 times daily, it will be switched to a basal insulin alone and Glargine was given at 40% of total daily dose of pre-mixed insulin. The dose will be gradually increased until fasting BG of 80-130mg/dl is achieved by using the self-titration regimen. (Attachement#1)
- (4) Metformin at home dose will be continued, but other non-insulin diabetes medications will be discontinued. If the patient is not on metformin, then Metformin ER will be started at 500mg daily with a meal for 2 weeks and then 1000mg daily as a maintenance dose if tolerated.
- (5) Both SGLT2i, Empagliflozin 10 mg or 12.5mg once daily, and GLP1 RA, Dulaglutide 0.75mg subcutaneously once weekly, will be added to metformin and a basal insulin.

The patients will be trained on the injection technique of the once-weekly GLP1 RA and given information on potential side effects, risk and benefits of all new medications in detail, hypoglycemia management and the self-titration regimen for the basal insulin.

In the control group, the patients will be advised to remain on MDI and to have the usual and standard care through the primary care provider. They will also be advised to gradually increase the basal insulin until fasting BG of 80-130mg/dl is achieved by using the self-titration regimen as in the intervention group. (Attachement#1)

The patients in both groups will be advised to monitor FPGs daily at minimum.

A research coordinator will make a phone call to all participants in both groups at week 1, 2, 8, and 12 to review fasting glucose measurements, ask for possible adverse events, incidents of hypoglycemia, and any change in medication.

At each visit, the patients will be questioned for adverse events (nausea, vomiting, diarrhea, headache, acute pancreatitis, bacterial or fungal genito-urinary tract infection, severe hypoglycemia with blood glucose <40, mild hypoglycemia with BG 41-69, diabetes ketoacidosis, any hospitalization for hyper or hyper-glycaemia).

At 2nd visit, Empagliflozin and GLP1 RA, Dulaglutide will be increased to maximum doses of 25mg and 1.5mg respectively if the patient tolerated the starting dose and if the additional glycemic control is required.

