#### ***Inclusion criteria***

The patients with T2DM who met all of the following criteria were included in the study.

- (1) > 21 years of age
- (2) Body mass index (BMI)  $\geq 30$  kg/m^2
- (3) On insulin at least 2 times daily comprising both a basal and a prandial insulin or a pre-mix insulin with or without other non-insulin medications for a least past 3 months
- (4) A1c >8%
- (5) eGFR >45%

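### Do the different stopping points for basal-insulin titration undermine the week-16 A1c comparison?

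*Combined protocol and SAP*

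**What the plan says.** Three titration rules stand in the Procedures section, and all cite Attachment 1.

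- **Intervention, item 2 (basal plus prandial users).** Basal insulin "will be continued at 80 % of the home dose". Then: "The dose will be gradually increased until the patient is back on the home dose", with the alternative stop "or fasting BG of 80-130mg/dl was achieved by using the self-titration regimen".
- **Intervention, item 3 (pre-mix users).** They are switched to basal insulin alone: "Glargine was given at 40% of total daily dose of pre-mixed insulin". Then: "The dose will be gradually increased until fasting BG of 80-130mg/dl is achieved by using the self-titration regimen". No home-dose stop is given.
- **Control.** Patients stay on their multiple-injection regimen under usual care from their own provider and are advised to "gradually increase the basal insulin until fasting BG of 80-130mg/dl is achieved by using the self-titration regimen as in the intervention group". No home-dose stop is given.

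Inclusion criterion 3 admits both kinds of insulin user: "On insulin at least 2 times daily comprising both a basal and a prandial insulin or a pre-mix insulin". The primary outcome (Outcome measurements) is the change in A1c at week 16. The Statistical Analysis section plans no breakdown by prior insulin type and no summary of the insulin dose reached.

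**The concern.** Read literally, item 2 lets a patient stop at the home dose while still above the fasting target. A control patient on the same kind of insulin has no such ceiling, although the control rule claims to follow the intervention arm. In addition, a control patient on pre-mix has no separate basal insulin to increase, so the control instruction has no obvious meaning for that patient.

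If titration was meant to be common to both arms, the A1c difference would combine the change of regimen with a difference in titration effort. The ceiling would work against step-down among basal-prandial users. Among pre-mix users, having a titratable basal insulin in one arm only might work in its favour. The net effect would depend on the mix enrolled. The trial is open-label and patients titrate themselves, so the written instruction matters, and no planned table would show the imbalance.

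**Working it through.** **1. The rules side by side.**

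| Group | Starting basal dose | Home-dose stop | Fasting 80-130 mg/dl stop |
|---|---|---|---|
| Intervention, basal-prandial (item 2) | 80% of home dose | yes | yes |
| Intervention, former pre-mix (item 3) | 40% of total pre-mix dose | no | yes |
| Control | home dose (patient stays on current regimen) | no | yes |

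Only item 2 stands apart; item 3 and the control rule share one end-point. Part of the split by insulin type is structural, because a pre-mix user has no separate basal home dose to return to.

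**2. What the linking phrase can mean.** Controls begin at their home dose. A home-dose stop would end their titration before it began and leave the instruction empty. The phrase therefore most naturally points to the algorithm in Attachment 1, which items 2 and 3 also cite, and not to item 2's stopping point. Attachment 1 is not in the text available for review and might settle this.

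**3. The plan's own sample size.** Inputs from Statistical Analysis: baseline A1c 8.5, SD 1, decline 12-15%, 80% power, two-sided 5%, 20 per arm. Assumptions: no change in control, and SD 1 applies to the analysed outcome.

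- Differences: 8.5 × 0.12 = 1.02 and 8.5 × 0.15 = 1.275.
- n per arm = 2 × (1.960 + 0.842)² × SD² / difference². This gives 15.70/1.040 = 15.1, so 16, and 15.70/1.626 = 9.7, so 10. The t-test gives 17 and 11.

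The stated 20 is not reproduced exactly; it exceeds what the inputs require. It would follow from 16/0.8 = 20, but no dropout rate is stated.

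**4. How large would a shift have to be?** Power from the noncentral t with 38 degrees of freedom and noncentrality = difference/√(2/20) = difference/0.316. The shifts against step-down are assumed; the documents supply none.

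| Assumed shift | Planned 1.02: remaining difference, power | Planned 1.275: remaining difference, power |
|---|---|---|
| 0 | 1.02, 88.2% | 1.275, 97.5% |
| 0.1 | 0.92, 80.9% | 1.175, 95.2% |
| 0.2 | 0.82, 71.5% | 1.075, 91.2% |
| 0.3 | 0.72, 60.2% | 0.975, 85.2% |

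The difference giving exactly 80% power at 20 per arm is 0.909. The margin is 1.02 − 0.909 = 0.11 at the low end and 1.275 − 0.909 = 0.37 at the high end.

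**5. Would a breakdown by prior insulin type help?** The mix is not stated. If a stratum held 5, 10 or 15 patients per arm, the 95% half-width for its difference would be t × √(2/n):

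- n = 5: 2.306 × 0.632 = 1.46
- n = 10: 2.101 × 0.447 = 0.94
- n = 15: 2.048 × 0.365 = 0.75

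Against a planned difference of about 1, such a table could only be descriptive.

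**The case for a change.** The best case for acting is that the text is uneven and tidying it is cheap. The protocol never says that item 2's home-dose stop is a deliberate part of stepping down. Entry requires A1c above 8% on current insulin, so some patients may be above the fasting target at their home dose, and there the ceiling could bind. At the low end of the planned effect, a 0.2-point shift would take power below 80%.

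The wording point stands: a reader cannot tell for certain whether item 2 is meant to differ from the control rule, or what a control on pre-mix should do. The inference to a compromised comparison does not stand.

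- The step-down arm is a package: prandial insulin stopped, basal insulin reduced and re-titrated, non-insulin drugs other than metformin stopped, two new agents added. Its comparator is continued injections with usual care. Basal dosing is part of each assigned strategy, and randomisation supports attributing the difference to the package. The documents state no aim of isolating one component at equal titration.
- A bias towards step-down among pre-mix users is not shown, because usual care leaves room for their provider to adjust doses.
- The shifts used for the power illustration have no source in the documents, and at the upper end of the planned effect power stays above 80% for all three.
- A dose table is more than a wording change. The calls ask about changes in medication, but neither the visit assessments nor the call content explicitly lists insulin dose, so it could need new data collection.

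**Conclusion.** No change to design or analysis is needed. The remaining unevenness is one stopping rule that differs for one subgroup of one arm, an ambiguous cross-reference, and a missing detail for controls on pre-mix. Declaring that the end-points differ by design would alter nothing the trial does. Making them agree would be a clinical design choice with arguments on both sides. Reconciling the Procedures wording therefore belongs to the clinical team, and this review takes no view on which rule should apply.

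The size and net direction of any effect on the A1c contrast cannot be derived from the documents. The conclusion rests on reading the trial as a comparison of two whole strategies, which is how Design and Procedures describe it, and on the linking phrase referring to the Attachment 1 algorithm. Even if that second reading were wrong, the comparison of the strategies as written would remain interpretable.

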## Design

This is the prospective, randomized, open-label, controlled, parallel-group study. Patients will be allocated 1:1 to either intervention (i.e. Step-Down) or control (MDI) group by using block randomization with computer-generated random sequence from <http://www.randomization.com>.

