## Outcome measurements

The primary outcome is the change in A1c at the end of study period at week 16 and secondary outcomes are the changes in fasting blood glucose, weight, blood pressure, heart rate, fasting

lipids, serum sodium and potassium, serum creatinine, liver enzymes, CBC and Diabetes Medications Satisfaction (DM-SAT) scores at week 16.

Treatment satisfaction will be measured using the Diabetes Medication Satisfaction Tool (DM-SAT).

The DM-SAT measures satisfaction with the patient's diabetes medications regimen. The instrument consists of 16 items which create 4 subscales (3 items for wellbeing, 3 items for medical control, 5 items for lifestyle, and 5 items for convenience) and a total score. Responses are summed and converted to a score from 0 to 100 for each subscale and overall, with higher scores representing more satisfaction.

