### **Statistical Analysis:**

We will attempt to recruit and consent 20 patients in each arm that was calculated to provide an 80% statistical power at a 0.05 alpha in this continuous endpoint, two independent sample study.

The calculation was based on the following:

A mean Hemoglobin A1c of  $8.5 \pm 1\%$  at the initiation of the study period. In the treatment group we anticipate a decline in Hemoglobin A1c of 12-15% by the end of the study period. The standard deviation for the mean A1c was derived from the literature (Glucagon-Like Peptide 1 Receptor Agonist or Bolus Insulin With Optimized Basal Insulin in Type 2 Diabetes. Michaela Diamant Et al. Diabetes Care October 2014 vol. 37 no. 10. 2763-2773)

The data will be analyzed by using SPSS or similar software. Significance testing will be conducted at the two-sided 5% level. Continuous variables will be examined for normality and if assumption is met, differences in mean values will be tested using Student's t test an analysis of variance (ANOVA). If not normally distributed, non-parametric procedures will be used, including Wilcoxon rank Sum test. Categorical data will be analyzed using Fisher's exact test and Chi square analysis. Since before/after comparisons will also be performed on the same study patients, we will utilize paired t tests and McNemar's chi-square test.

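### At visits hypoglycaemia is graded by glucose reading alone, while testing beyond one fasting value a day is neither scheduled nor counted, so a by-arm tally of low readings may partly reflect how often each arm tests

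*Combined protocol and SAP*

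**What the plan says.** **Testing.** Procedures sets a floor for both arms: "The patients in both groups will be advised to monitor FPGs daily at minimum". The text supplied gives no schedule for other times of day and no upper limit, and it does not say that the number of tests is recorded. Attachment #1, the self-titration regimen cited for both arms, is not in that text.

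**Definition.** The visit adverse-event list in Procedures grades the event as "severe hypoglycemia with blood glucose <40, mild hypoglycemia with BG 41-69". It has no criterion for symptoms or for help from another person, and a reading of exactly 40 falls in neither class.

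**Collection.** At weeks 1, 2, 8 and 12 a coordinator telephones "to review fasting glucose measurements, ask for possible adverse events, incidents of hypoglycemia, and any change in medication". No threshold is attached to that question. Visits at weeks 4 and 16 use the graded list.

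**Regimens.** Design states: "This is the prospective, randomized, open-label, controlled, parallel-group study". In the step-down arm, "All prandial insulin injections (Humalog, Novolog, Apidra, Novolin R or Humulin R) will be discontinued", and pre-mixed insulin is replaced by basal insulin. In the control arm, "the patients will be advised to remain on MDI and to have the usual and standard care through the primary care provider".

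**Analysis.** Outcome measurements names change in A1c as primary, and its secondary list ends with "lipids, serum sodium and potassium, serum creatinine, liver enzymes, CBC and Diabetes Medications Satisfaction (DM-SAT) scores at week 16". Hypoglycaemia is in neither. Statistical Analysis has only a general sentence that could cover it: "Categorical data will be analyzed using Fisher's exact test and Chi square analysis".

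**The concern.** If any reading below 70 counts as an event, the number of events found depends on how many readings are taken. Randomization does not balance this, because testing follows from the assigned regimen. A patient who still doses insulin at meals has a reason to test at meals, and a patient on basal insulin plus a weekly injection has less. The call question is not limited to fasting values, and the visit list has no time-of-day limit, so non-fasting lows count.

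The title asks whether step-down is the better option, and less hypoglycaemia is an obvious argument for saying so. Hypoglycaemia is asked about at all six on-treatment contacts, by name on every call and graded by severity at visits. If the MDI arm tested more, the MDI tally would rise even with identical true risk. If follow-up ends without test counts or symptoms on record, no later analysis can separate risk from testing.

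**Working it through.** The documents give no hypoglycaemia rate, no testing frequency and no share of lows noticed through symptoms, so there is no plan figure to reproduce. The calculation below only shows how far the answer depends on these unknowns.

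**Inputs from the documents:** 20 per arm and a two-sided 5% level (Statistical Analysis); 16 weeks = 112 days (Procedures); one test a day as the floor (Procedures).

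**Assumptions:** equal true risk in both arms. Step-down patients test once a day and 20% of them have at least one reading below 70. MDI patients test k times a day. A share s of step-down lows is found through symptoms whatever the testing. A non-fasting test is w times as likely as a fasting test to show a low.

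**Formulas.** Cumulative hazard in step-down: H = -ln(1 - 0.20) = 0.2231, which is a chance per daily reading of 1 - 0.8^(1/112) = 0.00199. For MDI:

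P(at least one low) = 1 - exp(-H × [s + (1 - s)(1 + w(k - 1))])

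Example with s = 0, w = 1, k = 3: 1 - exp(-0.2231 × 3) = 0.488.

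With gamma frailty of variance 1, H = 0.25 keeps step-down at 20%, and with w = 1 the MDI proportion is 1 - 1/(1 + 0.25 × [s + (1 - s)k]).

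Rejection is the exact probability that a two-sided Fisher test gives p < 0.05 with 20 per arm, against 0.20 in step-down.

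| Setting | MDI patients with a low, k = 2 / 3 / 4 | Rejection, k = 2 / 3 / 4 |
|---|---|---|
| s = 0, w = 1 | 36% / 49% / 59% | 13% / 38% / 63% |
| gamma frailty, s = 0, w = 1 | 33% / 43% / 50% | 9% / 25% / 41% |
| s = 0.5, w = 1 | 28% / 36% / 43% | 5% / 13% / 25% |
| s = 0, w = 0.5 | 28% / 36% / 43% | 5% / 13% / 25% |
| gamma frailty, s = 0.5, w = 1 | 27% / 33% / 38% | 4% / 9% / 17% |
| s = 0.75, w = 1 | 24% / 28% / 32% | 3% / 5% / 8% |
| s = 0, w = 0.25 | 24% / 28% / 32% | 3% / 5% / 8% |

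With equal testing (k = 1) the test rejects in 2% of trials. In the first row nearly all rejections go against MDI.

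The base rate matters too. With s = 0, w = 1 and k = 4, a 10% base gives 34% of MDI patients with a low and 35% rejection. A 30% base gives 76% and 76%.

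**Cross-check with a different model.** Let both arms have the same true mean of 1, 2 or 4 episodes per patient, with a detection probability d for each episode. The proportion recorded is 1 - exp(-mean × d). With d = 30% in both arms, rejection is about 2%. With 50% on MDI and 30% on step-down, the recorded rate ratio is 50/30 = 1.67 and rejection is 9% to 15%. With 60% and 20%, the ratio is 3.0 and rejection is 35% to 66%. These detection probabilities are assumed as well.

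**The case against.** **No hypoglycaemia comparison is planned.** It is not a listed outcome, and the general sentence on categorical data does not name it. This stands. A reader might infer that a prespecified comparison is biased, but the documents specify none. The rejection rates describe a test someone might run, not one the plan assigns.

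**The glucose-only definition does not cover every contact.** The four calls ask about incidents without a threshold, so symptomatic events without a reading can be reported there. This stands. It also means that calls and visits do not ask the same question.

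**Attachment #1 might set further testing.** It cannot be checked. The main text cites it only for basal titration to a fasting target.

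**The testing gap is inferred, and its direction is not certain.** Both arms receive the same testing advice and titrate to the same fasting target. The hypoglycaemia-management training is described directly after the intervention changes and may apply to step-down only, which could raise testing or reporting there. A near-low reading can also prompt food or a smaller dose and so prevent an event. All of this stands. It limits what can be said about direction and size, but it does not make the two arms' counts comparable.

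**The larger figures need strong assumptions.** They need no detection through symptoms and the same chance of a low at every hour. This stands: if a non-fasting test is a quarter as likely to show a low, rejection falls to 3%, 5% and 8%.

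**Part of any excess on MDI may be real,** since meal insulin can itself cause lows. This is also true, and it is why asymptomatic daytime lows should be shown rather than dropped.

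**Conclusion.** The point holds in a limited form. With visit grading by glucose alone, a testing floor without a schedule and no record of test counts, a by-arm tally of all low readings cannot be read as a comparison of hypoglycaemia risk. The likely direction favours step-down, on the assumption that patients dosing meal insulin test more.

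The size is unknown. At a 20% base rate the settings shown give rejection of about 3% to 63% under equal true risk. These are illustrations, not bounds, and every rate behind them is assumed.

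Two stronger readings are tempting. One is that the bias is known to be large and to favour the intervention; the documents contain no testing or event rates to support that. The other is that the trial's main result is compromised; A1c is measured from a blood test at each visit and does not depend on home glucose testing.

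**What to change.** Record three items on the existing call and visit form, with the same questions at calls and visits:

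1. for each low, whether it was the fasting reading or another one;
2. whether there were symptoms, or another person's help was needed;
3. the number of glucose tests in the past week.

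Add to Outcome measurements a descriptive safety summary by arm, with exact 95% confidence intervals for the patient proportions:

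- (a) patients with at least one required fasting reading below 70;
- (b) patients with at least one symptomatic or assisted episode, with or without a glucose value;
- (c) all readings below 70, shown beside tests per week.

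Class any episode needing another person's help as severe whatever the glucose, and set the severe cut-off to ≤40 so that a reading of 40 is classed. State that a claim of less hypoglycaemia will not rest on (c) alone.

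The cost is three form items and one paragraph, with no added visit, blood test or glucose test. The weakness is that (b) relies on self-report in an open-label trial, which is why all three counts should be shown together.

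### Visits define and grade hypoglycaemia by glucose value alone and calls use no definition, so lows needing another person's help are not captured as such and unmeasured lows may be recorded inconsistently

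*Combined protocol and SAP*

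**What the plan says.** The adverse-event list in Procedures, used at each visit, contains two hypoglycaemia items: "severe hypoglycemia with blood glucose <40, mild hypoglycemia with BG 41-69". A glucose value is the only criterion for either. Nothing in the document refers to symptoms of a low, to help from another person, or to a low treated without a meter reading. The one nearby item that needs no reading is "any hospitalization for hyper or hyper-glycaemia".

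The calls at weeks 1, 2, 8 and 12 are worded differently. The coordinator is to "review fasting glucose measurements, ask for possible adverse events, incidents of hypoglycemia, and any change in medication". No threshold or grade is attached.

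On self-monitoring, Procedures states: "The patients in both groups will be advised to monitor FPGs daily at minimum". This is one shared floor. No non-fasting schedule is set for either arm.

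The arms differ in mealtime insulin. For step-down, "All prandial insulin injections (Humalog, Novolog, Apidra, Novolin R or Humulin R) will be discontinued"; for control, "the patients will be advised to remain on MDI". The Design section states: "This is the prospective, randomized, open-label, controlled, parallel-group study". Outcome measurements does not list hypoglycaemia as a primary or secondary outcome, and Statistical Analysis names only general tests for categorical data.

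**The concern.** The study title asks whether stepping down is the better option. One arm stops prandial insulin, the other keeps it, and both self-titrate basal insulin towards the same fasting target. A reader will want to compare lows between the arms, and above all the lows a patient could not manage alone. The visit items cannot supply that comparison because they record a number and not what happened to the patient.

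The change of wording between calls and visits adds a second problem. Whether an unmeasured low enters the record may depend on which contact happens to follow it. If details of symptoms and help are not asked for at the time, they may not be recoverable when the data are analysed.

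**Working it through.** The plan gives no figure on this point, so there is none to reproduce. The check has three parts.

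**1. The two rules applied to the same episodes.** The episodes are illustrative and say nothing about frequency.

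| Episode | Visit items, read literally | Call question |
|---|---|---|
| Reading 38, no symptoms | severe | may be reported, no grade |
| Reading below 40, helped by another person | severe | may be reported, no grade |
| Reading 45, helped by another person | mild | may be reported, no grade |
| Helped by another person, no reading | fits neither item | may be reported, no grade |
| Reading 52, self-treated | mild | may be reported, no grade |
| Symptoms, self-treated, no reading | fits neither item | may be reported, no grade |

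Rows 1 and 2 get the same grade although only one needed help. Rows 3 and 5 also get the same grade although only one needed help. Rows 4 and 6 can enter through a call but have no visit item. No contact, call or visit, asks whether help was needed, so that gap covers all 16 weeks.

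**2. How much of follow-up is reached only by a visit.** Inputs from Procedures: calls at weeks 1, 2, 8 and 12; follow-up visits at weeks 4 and 16. No recall period is stated, so two are assumed.

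- Each contact covers the time since the previous contact of either kind. Calls cover weeks 0-1, 1-2, 4-8 and 8-12: 1 + 1 + 4 + 4 = 10 weeks. Visits cover weeks 2-4 and 12-16: 2 + 4 = 6 weeks. 6/16 = 37.5%.
- Each call reaches back to the previous call. The week 8 call then covers weeks 2-8, and only weeks 12-16 rest on a visit alone. 4/16 = 25%.

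**3. What that could mean for the count.** Let u be the share of lows with no reading, which the documents do not give. If lows are spread evenly over time, and every unmeasured low in a visit-only window goes unrecorded, the share of all lows missed is u × visit-only share.

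| u (assumed) | × 0.25 | × 0.375 |
|---|---|---|
| 10% | 2.5% | 3.75% |
| 30% | 7.5% | 11.25% |
| 50% | 12.5% | 18.75% |

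These are upper figures for each u, because staff might write down an unmeasured low that a patient mentions.

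**The case against.** The strongest reply is that the visit list says what patients are asked, not what is thrown away. An unmeasured or assisted low could still be noted as an adverse event, the calls would pick up many such episodes, and the hospitalisation item may catch the worst. A glucose-based grade is also a legitimate choice, and the document never says that severe should mean assisted. Hypoglycaemia is not a listed outcome, and no comparison of it is specified.

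Much of this stands. The items are not wrong as glucose bands, and loss of unmeasured lows follows only from a strict reading. But nothing tells staff to record such episodes at visits or how to classify them, and the calls carry no grade. The hospitalisation item names only hyperglycaemia as printed. Even if one word was meant as hypoglycaemia, it would catch admitted patients only.

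Three stronger readings are tempting and not supported.

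- *Every assisted low is graded down or lost.* Not so: one with a reading below 40 is severe under the visit rule.
- *The count is biased between arms because MDI patients test more.* The documents give both arms the same minimum and no testing rates. Unequal testing above that floor is left open, not stated. The size of any effect depends on what is assumed. Take equal true risk, 4 versus 1 random tests a day, lows lasting 1 hour, and a share s of lows always prompting a test. The chance of recording a low is s + (1 − s)(1 − (23/24)^k) for k tests a day. The ratio is 0.157/0.042, about 3.8, at s = 0, but 0.789/0.760, about 1.04, at s = 0.75. Fasting-only testing in both arms could instead miss daytime lows in controls, so not even the direction is settled.
- *A fasting-only comparison between arms would solve this.* It would equalise scheduled readings but build in those missed daytime lows.

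**Conclusion.** The point holds in a limited form, and the change should be made. Visits grade hypoglycaemia by glucose value alone, calls ask about it without value or grade, and no contact records whether another person's help was needed. The severe count therefore does not capture assisted events with a reading of 41-69 or with no reading, and an unmeasured low may be recorded or not according to the contact that follows it.

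The size cannot be derived from the documents. The visit-only share of follow-up is 25% to 37.5% under the two recall periods assumed above. The resulting 2.5% to 18.75% of lows missed rests further on an assumed unmeasured share of 10% to 50%, an even spread of lows, and a strict reading of the visit list. The effect is on the safety description and on any comparison of lows between arms. The A1c primary analysis is untouched.

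**What to change.** In Procedures, put the same hypoglycaemia questions at every call and visit, and state the period each contact covers. For each episode record the glucose value if one was measured, whether there were symptoms, and whether another person's help was needed.

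In Statistical Analysis, add a sentence saying that hypoglycaemia will be reported by arm as:

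- (a) assisted episodes, whatever the glucose value;
- (b) reading-confirmed episodes in the plan's own glucose bands (a reading of exactly 40 lies in neither band as printed, so the sponsor must reconcile this);
- (c) symptom-only episodes without a reading, shown separately.

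Do not restrict the between-arm comparison to fasting readings. At most, show fasting and non-fasting readings side by side, so that a reader can see how far any difference rests on extra testing.

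The cost is two added questions (symptoms, help) on existing forms and one analysis sentence, with no new visits or tests. The drawback is that symptom-only episodes rest on patient recall in an open-label trial, which is why they belong in their own row.

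### After week 12, no named question would show a return to prandial or pre-mixed insulin, or outpatient care for high glucose, before the week-16 A1c

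*Combined protocol and SAP*

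**What the plan says.** All of the relevant text is in the combined protocol and SAP, mostly under Procedures.

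**Treatment change at the first visit, step-down arm.** "All prandial insulin injections (Humalog, Novolog, Apidra, Novolin R or Humulin R) will be discontinued". Basal insulin "will be continued at 80 % of the home dose" and is then titrated up. For pre-mix users, "Glargine was given at 40% of total daily dose of pre-mixed insulin", also followed by titration. Metformin is kept, or started if absent, while "other non-insulin diabetes medications will be discontinued". Empagliflozin and dulaglutide are both added at that visit. Each may be raised to its maximum dose at week 4 if tolerated and if more glycaemic control is needed.

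**Visits (baseline, weeks 4 and 16).** "At each visit, the patients will be questioned for adverse events", followed by a bracketed list. Low glucose appears there as "severe hypoglycemia with blood glucose <40, mild hypoglycemia with BG 41-69". High glucose appears as "diabetes ketoacidosis, any hospitalization for hyper or hyper-glycaemia".

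**Calls (weeks 1, 2, 8 and 12).** The coordinator is "to review fasting glucose measurements, ask for possible adverse events, incidents of hypoglycemia, and any change in medication".

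The description of the visits covers laboratory tests, vital signs, adverse-reaction questions and the satisfaction questionnaire. It contains no medication-change question.

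**The concern.** The trial asks whether patients poorly controlled on advanced insulin can be stepped down. Two direct signs that the step-down regimen is not holding are unscheduled care for high glucose and a return to prandial or pre-mixed insulin. Neither has its own item at the final visit. Hypoglycaemia, which a regimen with less insulin might be expected to reduce, has two graded items that need no contact with care. A safety table built from this list would describe low glucose in more detail than high glucose.

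A restart of insulin is foreseeable. The protocol text gives no rescue rule and no hyperglycaemia threshold, and it specifies no escalation of the two new drugs after week 4. For step-down patients who were not on pre-mix, basal titration may end at the previous home dose even if the fasting target has not been reached.

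What is at stake is safety capture and interpretation. If an insulin restart in the last month is never asked about, the reader of the week-16 A1c cannot tell whether it was achieved on the step-down regimen. Events that were not collected cannot be recovered at analysis.

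**Working it through.** The plan gives no figure on this point to reproduce. The check is a count of the listed items and a reading of the contact schedule.

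**1. Items in the visit list (Procedures).** Nausea; vomiting; diarrhoea; headache; pancreatitis; genito-urinary infection; severe hypoglycaemia; mild hypoglycaemia; ketoacidosis; glycaemia-related hospitalisation. Total: 10.

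**2. Glucose items, under both readings of the hospitalisation wording.** The repeated word in "diabetes ketoacidosis, any hospitalization for hyper or hyper-glycaemia" is probably a slip for hypo or hyper.

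| | As printed | Read as hypo or hyper |
|---|---|---|
| Low-glucose items | 2 | 3 |
| of which need no care | 2 | 2 |
| High-glucose items | 2 | 2 |
| of which ketoacidosis or admission | 2 | 2 |
| Items for non-admitted hyperglycaemia | 0 | 0 |

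The last row, on which the point rests, is the same under either reading.

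**3. What is named at each contact after baseline.**

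| Week | Contact | Adverse-event question | Medication-change question |
|---|---|---|---|
| 1 | Call | Open, plus hypoglycaemia | Yes |
| 2 | Call | Open, plus hypoglycaemia | Yes |
| 4 | Visit | Listed items | Not named |
| 8 | Call | Open, plus hypoglycaemia | Yes |
| 12 | Call | Open, plus hypoglycaemia | Yes |
| 16 | Visit | Listed items | Not named |

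**4. Which gap matters.** A change made around week 4 falls between the calls at weeks 2 and 8, so the week-8 question covers it. A change after the week-12 call has no later named question. Uncovered interval: 16 − 12 = 4 weeks; 4/16 = 25% of follow-up. It ends at the primary endpoint.

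**5. Size of the first-visit insulin change.** Prandial insulin: 100% stopped. Basal: 1 − 0.80 = 20% lower at the start. Pre-mix users: 1 − 0.40 = 60% lower in total daily insulin. The last figure has a different denominator from the first two, so they should not be compared directly. All are starting values before titration and before any effect of the added drugs. They show why the question is relevant and do not measure hyperglycaemia.

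**6. Number of events missed.** The documents give no rate for outpatient hyperglycaemia care or for insulin restarts, so this cannot be estimated.

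**The case against.** The strongest reply is that high glucose is already well watched. Both arms are advised to check fasting glucose at least daily, and those readings are reviewed at four calls. The calls ask openly about adverse events and medication changes. A1c and the metabolic panel are taken at every visit, and fasting glucose is a secondary outcome. This stands, and it rules out any claim that hyperglycaemia goes unmonitored. It does not close the gap, because these measures show level of control. They do not show whether a patient sought care or went back to prandial insulin, and the minimum home monitoring is fasting only, whereas prandial insulin acts on meals.

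A second reply is that step-down is a substitution. That is correct: two drugs are added on the same day, with metformin if absent, and there is a planned increase at week 4. A reader who saw only the insulin reductions might infer unprotected withdrawal, and the text does not support that. Whether the new drugs compensate is what the trial tests.

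A third reply is that the call script, the adverse-reaction form and Attachment 1 are not among the documents and may already ask these questions. That is possible. The point is confined to the protocol text.

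Finally, with a planned 20 patients per arm, any counts will be small and will only describe what happened. That also stands.

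**Conclusion.** The point holds as a minor one. The protocol names no item for hyperglycaemia treated without admission (0 of 10 visit items). Its last named open adverse-event and medication-change questions are at week 12, 4 weeks before the primary A1c. The visit adverse-event list is still asked at week 16, but it does not cover either event.

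Three stronger readings are tempting and are not supported:

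- **Both post-baseline visits leave a hole in medication-change capture.** Only week 16 does, since the week-8 call covers the period around week 4.
- **The primary comparison is biased.** Nothing in the documents shows a bias or its direction. The A1c measurement itself is unaffected.
- **The list was drawn up to favour step-down.** The uneven detail is a fact of the wording, and the documents say nothing about intent. No by-arm event table is prespecified for it to distort.

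The conclusion assumes that the forms not supplied follow the protocol text. If they already contain these questions, one confirming sentence in Procedures would settle the matter.

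**What to change.** In Procedures, with the same wording in both arms and at contacts that already exist:

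- **(a)** Add one item to the visit list and to the calls: *any unscheduled clinic, urgent-care or emergency visit for hyperglycaemia, whether or not hospitalised*. Define unscheduled to exclude study visits and pre-booked usual-care appointments, because control patients are followed by their primary care provider.
- **(b)** Ask the medication-change question at the week-16 visit as well as at the calls. Record drug, date and reason, so that a restart of prandial or pre-mixed insulin in step-down can be told apart from planned basal titration.
- **(c)** In Statistical Analysis, state that both will be reported descriptively by arm beside hypoglycaemia, with no significance test.

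The cost is one added item and one existing question repeated at one existing visit, with no new visits, blood tests or fingersticks. The downsides are a slightly longer form, a possibly less favourable event table for step-down, and care-seeking that may differ by arm because the trial is open-label. That last limit is the reason for reporting the counts without a test.
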